#### 9.7.2. Cohort Study

##### 9.7.2.1. Propensity Score Modeling and Matching

The COMIRNATY 2023-2024 Formula-exposed and the unexposed comparator cohorts will be created as described in [Section 9.2.3](#). Each cohort member will be described with respect to baseline covariates as listed in [Section 9.3.3](#). These cohort members will be included in the propensity score modeling and matching.

This study will use a single PS model that encompasses risk factors for multiple outcomes, an approach demonstrated in other studies conducted to fulfill post-licensure regulatory commitments and requirements to the FDA and other regulatory agencies ([Seeger et al., 2023](#); [Ziyadeh et al., 2020](#)). While not all risk factors may be associated with all outcomes to the same degree, adjusting for covariates that are weakly or not at all associated with a given outcome is expected to result in negligible bias if residual confounding is small ([Brookhart et al., 2006](#); [Myers et al., 2011](#)). Incorporating a wide array of outcome predictors

(Section 9.3.3) into the PS is expected to minimize residual confounding, producing groups with similar patterns of both measured and unmeasured factors (Guertin et al., 2016).

The PS model will consist of a logistic regression model that incorporates the pre-specified demographic and comorbidity covariates, healthcare utilization, and calendar month of vaccination or cohort entry as independent variables, and an indicator for receipt of the COMIRNATY 2023-2024 Formula as the dependent variable. Two-way interactions of all variables with calendar month of vaccination or cohort entry, or empirically defined variables that are potential confounders, may also be considered for inclusion in the following model:

$$\begin{aligned} & \text{logit}\{P(T_i = 1 \mid \mathbf{X}_i)\} \\ &= \beta_0 + \beta_1 \text{Sex (binary)}_i + \beta_2 \text{Age (categorical)}_i \\ &+ \beta_3 \text{Calendar month (categorical)}_i + \beta_4 \text{Geographic region (categorical)}_i \\ &+ \beta_5 \text{Asthma (binary)}_i + \beta_6 \text{Non-malignant blood disorders (binary)}_i \\ &+ \beta_7 \text{Chronic lung disease (binary)}_i + \beta_8 \text{Down syndrome (binary)}_i \\ &+ \beta_9 \text{Heart disease (binary)}_i \\ &+ \beta_{10} \text{History of SARS-CoV-2 infection (binary)}_i \\ &+ \beta_{11} \text{Immunocompromised status (binary)}_i \\ &+ \beta_{12} \text{Kidney disorders (binary)}_i + \beta_{13} \text{Liver disorders (binary)}_i \\ &+ \beta_{14} \text{Neurological or neurodevelopmental conditions (binary)}_i \\ &+ \beta_{15} \text{Malignant neoplasms (binary)}_i + \beta_{16} \text{Obesity (binary)}_i \\ &+ \beta_{17} \text{Type II diabetes (binary)}_i \\ &+ \beta_{18} \text{Number of hospitalizations in prior year (continuous)}_i \\ &+ \beta_{19} \text{Number of emergency room visits in prior year (continuous)}_i \\ &+ \beta_{20} \text{Number of outpatient encounters in prior year (continuous)}_i \\ &+ \beta_{21} \text{Seasonal influenza vaccination (binary)}_i \\ &+ \beta_{22} \text{RSV vaccination (binary)}_i + \beta_{23} \text{Systemic immunomodulators (binary)}_i \\ &+ \beta_{24} \text{Oral corticosteroids (binary)}_i + \beta_{25} \text{Antivirals (binary)}_i \\ &+ \beta_{26} \text{Antibiotics (binary)}_i + \beta_{27} \text{Identified empiric variables (binary)}_i, \end{aligned}$$

where  $T_i$  denotes exposure status for individual  $i$ , with  $T_i = 1$  indicating a recorded vaccination of the COMIRNATY 2023-2024 Formula and  $T_i = 0$  indicating no recorded vaccination of the COMIRNATY 2023-2024 Formula.

A greedy digit-based matching algorithm will be used, in which patients exposed to the COMIRNATY 2023-2024 Formula are matched without replacement to comparator patients at a given level of precision defined by the number of digits of the PS (Parsons, 2001), to a maximum of 8 decimal places. When no further matches are available at a given level of precision, the number of digits is sequentially reduced until a maximum allowable caliper of 0.1 is reached, thereby ensuring that the matched cohorts are comparable with respect to the underlying measured risk factors. Matching by propensity score will be conducted within

strata defined by age group and calendar period. A matching ratio (e.g., up to 1:10) may be implemented.

PS matching will produce a single matched cohort (the master cohort) that will be used to conduct all primary, secondary, and sub-group analyses for the study outcomes. Balance between the PS-matched cohorts will be evaluated by overlaying graphs of the PS distributions in COMIRNATY-exposed and comparator cohorts before and after PS matching. Additionally, standardized differences between the PS-matched cohorts for each covariate in the model will also be assessed. Variables with an absolute standardized difference less than 0.1 will be considered balanced (Austin, 2009). If a variable has a standardized difference that is greater than 0.1, further PS model modifications (e.g., addition of interaction terms) or inclusion of the imbalanced covariates in an outcome model will be considered (Normand et al., 2001). If there are confounders identified that would only be appropriate to include for one outcome and not the others, a separate PS model for the specific outcome will be considered.

Outcome-specific exclusion criteria will be applied to the master cohort after PS matching but before the outcome specific analysis; the matched cohort that remains will be the analytic cohort for that specific outcome. The matched comparators of individuals excluded for outcome-specific exclusion criteria will also be excluded from the outcome-specific analysis.

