### 9.3.3. Covariates

All members of the study cohorts will be described according to covariates identified in the claims data. Demographic attributes will be determined on the vaccination/cohort entry date, while other factors will be assessed in the one year prior to the cohort entry date. Unless specified as for descriptive purposes only, the covariates listed will be included in the PS models. All variables are binary unless otherwise specified.

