#### Demographic Attributes

- Sex
- Age (categorical); for the purposes of matching the exposed and unexposed cohorts in Phase 2, we will use the following age groups: 6 months–4 years, 5–11 years, 12–17 years, 18–64 years, and ≥ 65 years
- Calendar month of the vaccination date or cohort entry date (categorical)
- Geographic region (categorical)

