#### **Medication History**

- Systemic immunomodulators
- Oral corticosteroids
- Antivirals
- Antibiotics

In addition to the covariates listed above, baseline attributes will be identified on an empiric basis by examining the 25 most frequently occurring diagnoses, drugs dispensed, and procedures (including other baseline vaccinations, as captured through NDC and CPT codes) performed among individuals with and without COMIRNATY 2023-2024 Formula exposure.

These empiric covariates will be considered for inclusion in the PS models if they are potential confounders.

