#### 9.7.2.4. Subgroup Analysis

If sample size permits, the main analysis will be restricted to the following subgroups:

- Individuals with concomitant administration of a non-COVID-19 vaccine (e.g., seasonal influenza, RSV) on cohort entry date; specific analyses will be performed among individuals receiving seasonal influenza vaccine and those receiving RSV vaccine
- Immunocompromised individuals
- Individuals with specific baseline comorbidities, such as a chronic lung, heart, kidney or liver condition; cancer; Down syndrome or other neurological or neurodevelopmental disorders; and blood disorders
- Individuals with prior SARS-CoV-2 infection
- Individuals with prior COVID-19 vaccination
- Pregnant women
- Individuals aged < 18 years
- Individuals aged  $\geq$  65 years

For the subgroup analysis, the propensity score will be included in the model as a covariate, given that some matched strata may be broken by restricting both the COMIRNATY 2023-2024 Formula cohort and the comparator cohort by the above attributes. As with the primary analysis, unconditional Poisson regression will be used, and the model will account for individuals who are included in both groups.

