Lastly, a descriptive analysis of the matched cohorts will focus specifically on outcomes related to pregnancy (spontaneous abortion, stillbirth, preterm birth, major congenital malformations and small for gestational age). Recipients of the COMIRNATY 2023-2024 Formula and comparators who are pregnant at cohort entry will be identified, and the timing of their vaccination in relation to their last menstrual period (LMP) will be characterized. Baseline characteristics will be descriptively compared among the pregnant COMIRNATY 2023-2024 Formula recipients and comparators. Among COMIRNATY 2023-2024 Formula recipients who are pregnant at cohort entry, as well as among pregnant comparators, the incidence of pregnancy outcomes (spontaneous abortion, stillbirth, preterm birth) during follow-up will be described. For those individuals whose pregnancy results in a live birth, the prevalence of major congenital malformations and small for gestational age in their infants will be descriptively reported. Prevalence estimates will be reported separately for infants whose mothers received the COMIRNATY 2023-2024 Formula when pregnant and infants whose mothers do not have a recorded vaccination of COMIRNATY 2023-2024. Due to the relatively short length of follow-up, comparative analyses relating to pregnancy and infant outcomes will not be performed.

All results from Phase 2 analyses will be presented in the Final Report.

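### Pregnancy at cohort entry, which the study already identifies, is in neither the propensity score nor its balance check

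*Protocol*

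**What the plan says.** Section 9.3.3 lists the covariates and ties them to the score: "Unless specified as for descriptive purposes only, the covariates listed will be included in the PS models". Pregnancy is not on the list, even as a descriptive item.

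Section 9.7.2.1 describes the model in words ("The PS model will consist of a logistic regression model that incorporates the pre-specified demographic and comorbidity covariates, healthcare utilization, and calendar month") and then prints it term by term, from β1 to β27. No term is pregnancy. The last is an open slot for empirically chosen variables.

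For matching by age, Section 9.3.3 says "we will use the following age groups: 6 months–4 years, 5–11 years, 12–17 years, 18–64 years, and ≥ 65 years". All adults from 18 to 64 therefore form one stratum.

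Section 9.7.2.4 lists "Pregnant women" among the subgroups, if numbers allow. For the descriptive pregnancy analysis it adds: "Recipients of the COMIRNATY 2023-2024 Formula and comparators who are pregnant at cohort entry will be identified". Timing relative to the last menstrual period is also to be described.

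The balance check in Section 9.7.2.1 computes standardized differences for covariates in the model and treats an absolute value below 0.1 as balanced.

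**The concern.** The two cohorts enter by different doors. Recipients enter on a vaccination. Under Section 9.3.1.2, comparators enter on another vaccine or an outpatient encounter. Pregnancy affects both the use of care and the decision to be vaccinated, so its share could differ between the cohorts.

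The protocol relies on a single score intended to cover risk factors for many outcomes. Pulmonary embolism, cerebral venous sinus thrombosis and stroke are among those outcomes, and cohort follow-up runs for up to a year, so a woman pregnant at entry can contribute both pregnant and postpartum time. If pregnancy raises the rate of these events, a difference in its share would confound the Phase 2 rate ratio. The study would hold the variable needed to prevent this and not use it.

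Section 9.9 names three sources of residual confounding: the one-year lookback, prior COVID-19 vaccination, and vaccines other than influenza and RSV. Pregnancy is not mentioned.

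**Working it through.** The protocol gives no figure to reproduce here. The check has two parts.

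**Does anything in the plan bring pregnancy in?**

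- Covariate list and equation: no.
- Sex and age: both are in the model, but the 18–64 group does not isolate women of childbearing age.
- Utilization: counts of outpatient, emergency and hospital contacts may balance pregnancy in part. They do not identify it.
- Empiric step in Section 9.3.3: "baseline attributes will be identified on an empiric basis by examining the 25 most frequently occurring diagnoses, drugs dispensed, and procedures". Pregnancy codes might or might not rank that high in a cohort of all ages from 6 months. Variables found this way are only considered for inclusion.
- Outcome-specific score in Section 9.7.2.1: also only to be considered.
- Balance check: limited to model covariates. The rule in Section 9.7.2.2 that adds imbalanced covariates to the Poisson model depends on those standardized differences, so pregnancy would not trigger it.

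**How large could a bias be?** Let p1 and p0 be the shares pregnant among matched recipients and comparators, and k the event rate in pregnant or postpartum women relative to everyone else in the comparison. All three are assumptions; the documents give none of them.

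Bias factor = [1 + p1(k − 1)] / [1 + p0(k − 1)]

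Standardized difference = (p1 − p0) / √{[p1(1 − p1) + p0(1 − p0)] / 2}

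Example with p1 = 1%, p0 = 2%, k = 5: (1 + 0.01 × 4) / (1 + 0.02 × 4) = 1.04 / 1.08 = 0.963. The absolute standardized difference is 0.01 / √0.01475 = 0.082.

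| Recipients | Comparators | Abs. std. difference | k = 2 | k = 3 | k = 5 | k = 10 |
|---|---|---|---|---|---|---|
| 0.5% | 1% | 0.058 | 0.995 | 0.990 | 0.981 | 0.959 |
| 1% | 2% | 0.082 | 0.990 | 0.981 | 0.963 | 0.924 |
| 2% | 4% | 0.117 | 0.981 | 0.963 | 0.931 | 0.868 |
| 3% | 6% | 0.145 | 0.972 | 0.946 | 0.903 | 0.825 |

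If recipients are the more often pregnant, the factors invert: 2% against 1% at k = 5 gives 1.08 / 1.04 = 1.038.

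The choice of k matters as much as the shares. It must compare pregnant women with all non-pregnant people in the comparison, men and older adults included, not with non-pregnant women of the same age. Suppose the same-age ratio is 5 and the shares are 1.5% and 3%:

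- Young women's baseline rate one third of the group average: k = 5/3 = 1.67, and the factor is 1.010 / 1.020 = 0.990.
- One fifth: k = 1, and the factor is 1.00.
- One tenth: k = 0.5, and the factor is 0.9925 / 0.985 = 1.008.

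So even with the shares fixed, the sign can change.

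**The case against.** The strongest reply is that no imbalance has been shown. Matching uses sex, age group, utilization counts, influenza and RSV vaccination, obesity and diabetes, and these may remove part of any difference. The outpatient codes that qualify a comparator (Section 17.2.3) are general evaluation and management codes, with none labelled as maternity care, and some recipients may be vaccinated because they are pregnant. All of this stands. A reader might infer that pregnancy is left unbalanced and that comparators carry the excess, so that the vaccine looks safer than it is. The documents give no pregnancy share for either cohort and support neither step.

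A reader might also quote a bias for ages 18–64 from same-age relative risks. That uses the wrong reference group, and the plan contains no estimate for that age range: the primary rate ratio covers all ages, and the age subgroups are under 18 and 65 or over.

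It might further be inferred that the pregnant-women subgroup is confounded by the omission. Everyone in it is pregnant, so pregnancy status cannot confound it; at most, gestational timing could. The analysis of pregnancy and infant outcomes is descriptive only.

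Two limits on reach also stand. The self-controlled analysis covers the same clotting outcomes without a propensity score. And the descriptive pregnancy analysis will produce counts in both cohorts, so an imbalance might be noticed, although no rule links those counts to the outcome models.

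None of this answers the core point. The empiric and outcome-specific routes are discretionary, and a factor the study identifies is left to them. Nor can the gap be deferred to a later document: Section 7 calls this a combined protocol and analysis plan, and the equation is printed in full.

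**Conclusion.** The point holds as a gap in specification. Pregnancy at cohort entry is identified in both cohorts and defines a subgroup, but it is not a pre-specified covariate, not a named term in the score, and not covered by the balance check. An imbalance would be neither controlled by design nor detected by that check.

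The omission itself is certain from the text. That pregnancy raises the risk of pulmonary embolism, cerebral venous sinus thrombosis or stroke is a plausible assumption, not something the protocol states. Direction and size cannot be determined. Under the assumed shares in the table, the factor runs from 0.995 to 0.903 for k from 2 to 5 and reaches 0.825 at k = 10; it inverts if the shares are reversed, and moves close to or past 1 if young women's baseline rates are low. In the all-ages rate ratio the effect is probably small, because children and adults aged 65 or over dilute the pregnant share. The change is worth making because it is cheap, not because a material bias has been demonstrated.

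**What to change.** Add pregnancy status at cohort entry (yes or no, with trimester optional) to the covariate list in Section 9.3.3, to the equation in Section 9.7.2.1 and to the balance table. Define it in Appendix IV, which has no pregnancy-status list at present, and ascertain it in the same way in both cohorts.

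If the master cohort has already been matched, which the protocol does not say, the fallback is to report the standardized difference for pregnancy and to adjust the pulmonary embolism, cerebral venous sinus thrombosis and stroke models for it if it is imbalanced. This is weaker: shares of 1% and 2% give 0.082 and would pass the 0.1 rule.

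The cost is one more derived covariate and a short definition. The downside is some misclassification where pregnancy or the last menstrual period is inferred from later claims, since such a variable then depends partly on follow-up. The definition should say which claims it uses relative to cohort entry.

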#### Comorbidities

- Asthma
- Non-malignant blood disorders, including sickle cell disease
- Chronic lung disease, including chronic obstructive pulmonary disease (COPD)
- Down syndrome
- Heart disease
- History of SARS-CoV-2 infection
- Immunocompromised status (i.e., history of human deficiency virus [HIV]; organ, bone marrow or stem cell transplant; use of immunosuppressant medication)
- Kidney disorders, including chronic kidney disease
- Liver disorders
- Neurological or neurodevelopmental conditions
- Malignant neoplasms
- Obesity
- Type 2 diabetes

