#### **17.4.1.5. Heart Disease**

##### **17.4.1.5.1. ICD-10-CM Codes**

I01.0 Acute rheumatic pericarditis

I01.1 Acute rheumatic endocarditis

I01.2 Acute rheumatic myocarditis

I01.8 Other acute rheumatic heart disease

I01.9 Acute rheumatic heart disease, unspecified

I02.0 Rheumatic chorea with heart involvement

I05.0 Rheumatic mitral stenosis

I05.1 Rheumatic mitral insufficiency

I05.2 Rheumatic mitral stenosis with insufficiency

I05.8 Other rheumatic mitral valve diseases

I05.9 Rheumatic mitral valve disease, unspecified

I06.0 Rheumatic aortic stenosis

I06.1 Rheumatic aortic insufficiency

I06.2 Rheumatic aortic stenosis with insufficiency

- I07.0 Rheumatic tricuspid stenosis
- I07.1 Rheumatic tricuspid insufficiency
- I07.2 Rheumatic tricuspid stenosis and insufficiency
- I07.8 Other rheumatic tricuspid valve diseases
- I07.9 Rheumatic tricuspid valve disease, unspecified
- I06.8 Other rheumatic aortic valve diseases
- I06.9 Rheumatic aortic valve disease, unspecified
- I08.0 Rheumatic disorders of both mitral and aortic valves
- I08.1 Rheumatic disorders of both mitral and tricuspid valves
- I08.2 Rheumatic disorders of both aortic and tricuspid valves
- I08.3 Combined rheumatic disorders of mitral, aortic and tricuspid valves
- I08.8 Other rheumatic multiple valve diseases
- I08.9 Rheumatic multiple valve disease, unspecified
- I09.0 Rheumatic myocarditis
- I09.1 Rheumatic diseases of endocardium, valve unspecified
- I09.2 Chronic rheumatic pericarditis
- I09.81 Rheumatic heart failure
- I09.89 Other specified rheumatic heart diseases
- I09.9 Rheumatic heart disease, unspecified
- I11.0 Hypertensive heart disease with heart failure
- I11.9 Hypertensive heart disease without heart failure
- I13.0 Hypertensive heart and chronic kidney disease with heart failure and stage 1 through stage 4 chronic kidney disease, or unspecified chronic kidney disease

090177e1a5be86fe\Approved\Approved On: 19-Mar-2026 15:57 (GMT)

- I13.10 Hypertensive heart and chronic kidney disease without heart failure, with stage 1 through stage 4 chronic kidney disease, or unspecified chronic kidney disease
- I13.11 Hypertensive heart and chronic kidney disease without heart failure, with stage 5 chronic kidney disease, or end stage renal disease
- I13.2 Hypertensive heart and chronic kidney disease with heart failure and with stage 5 chronic kidney disease, or end stage renal disease
- I20.0 Unstable angina
- I20.1 Angina pectoris with documented spasm

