- I25.750 Atherosclerosis of native coronary artery of transplanted heart with unstable angina
- I25.751 Atherosclerosis of native coronary artery of transplanted heart with angina pectoris with documented spasm
- I25.758 Atherosclerosis of native coronary artery of transplanted heart with other forms of angina pectoris
- I25.759 Atherosclerosis of native coronary artery of transplanted heart with unspecified angina pectoris
- I25.760 Atherosclerosis of bypass graft of coronary artery of transplanted heart with unstable angina
- I25.761 Atherosclerosis of bypass graft of coronary artery of transplanted heart with angina pectoris with documented spasm
- I25.768 Atherosclerosis of bypass graft of coronary artery of transplanted heart with other forms of angina pectoris
- I25.769 Atherosclerosis of bypass graft of coronary artery of transplanted heart with unspecified angina pectoris
- I25.790 Atherosclerosis of other coronary artery bypass graft(s) with unstable angina pectoris
- I25.791 Atherosclerosis of other coronary artery bypass graft(s) with angina pectoris with documented spasm

090177e1a5be86fe\Approved\Approved On: 19-Mar-2026 15:57 (GMT)

- I25.798 Atherosclerosis of other coronary artery bypass graft(s) with other forms of angina pectoris
- I25.799 Atherosclerosis of other coronary artery bypass graft(s) with unspecified angina pectoris
- I25.810 Atherosclerosis of coronary artery bypass graft(s) without angina pectoris
- I25.811 Atherosclerosis of native coronary artery of transplanted heart without angina pectoris
- I25.812 Atherosclerosis of bypass graft of coronary artery of transplanted heart without angina pectoris
- I25.82 Chronic total occlusion of coronary artery
- I25.83 Coronary atherosclerosis due to lipid rich plaque
- I25.84 Coronary atherosclerosis due to calcified coronary lesion
- I25.89 Other forms of chronic ischemic heart disease
- I25.9 Chronic ischemic heart disease, unspecified
- I26.01 Septic pulmonary embolism with acute cor pulmonale
- I26.02 Saddle embolus of pulmonary artery with acute cor pulmonale
- I26.09 Other pulmonary embolism with acute cor pulmonale
- I27.1 Kyphoscoliotic heart disease
- I27.22 Pulmonary hypertension due to left heart disease
- I27.81 Cor pulmonale (chronic)
- I27.83 Eisenmenger's syndrome
- I27.9 Pulmonary heart disease, unspecified
- I30.0 Acute nonspecific idiopathic pericarditis
- I30.1 Infective pericarditis
- I30.8 Other forms of acute pericarditis
- I30.9 Acute pericarditis, unspecified

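### Phase 2 propensity score: several main vascular risk factors are not fixed covariates, although MI, PE, both strokes and CVST are outcomes

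*Protocol*

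**What the plan says.** Section 9.7.2.1 states that "This study will use a single PS model that encompasses risk factors for multiple outcomes" and expects the range of predictors in 9.3.3 to keep residual confounding small. The model "incorporates the pre-specified demographic and comorbidity covariates, healthcare utilization, and calendar month of vaccination or cohort entry as independent variables", and the equation is printed in full. Section 9.3.3 sets the rule for entry: "Unless specified as for descriptive purposes only, the covariates listed will be included in the PS models".

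The fixed terms are sex, age group, calendar month, region, 13 comorbidity flags, three utilization counts, influenza and RSV vaccination, and four drug classes (systemic immunomodulators, oral corticosteroids, antivirals, antibiotics). The last term in the equation is a placeholder for empiric variables. These come from the 25 most frequent diagnoses, drugs and procedures, and the rule is: "These empiric covariates will be considered for inclusion in the PS models if they are potential confounders".

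Balance is assessed by standardized differences for the covariates in the model, with 0.1 as the tolerance. A separate PS model may be considered where a confounder suits one outcome only. Section 7 describes the document as a combined protocol and SAP, and Annex 1 lists no standalone documents.

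**The concern.** A PS adjusts for what is in it and for what correlates with that. The fixed list includes antibiotics and Down syndrome, but not several of the main predictors of the five vascular outcomes, which does not fit the stated purpose of the single model.

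The comparison groups give these factors room to differ. Recipients enter on a vaccination date, whereas comparators can enter on any qualifying outpatient visit (9.3.1.2). Age is unlikely to stand in for them, because the only adult age groups the protocol gives are 18–64 and 65 or older.

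The balance check would not reveal the problem. An unlisted factor is not in the table, so the remedies in 9.7.2.1 and 9.7.2.2 (re-modelling, or adding the covariate to the Poisson model) would not be triggered. At stake is the credibility of Phase 2 rate ratios near 1, whether read as reassurance or as a modest excess.

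**Working it through.** **Step 1. Compare the outcomes with the covariate code lists (Annex 2, Appendix IV).**

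| Predictor | What the fixed covariates hold |
|---|---|
| Essential hypertension | None. The heart list has I11.x and I13.x (for example "Hypertensive heart disease without heart failure") but not I10 |
| Stroke/TIA, other cerebrovascular disease | None, apart from sickle-cell codes with cerebral vascular involvement under blood disorders. The neurological flag holds only F70–F89 |
| Prior venous thromboembolism | I26.01, I26.02 and I26.09 under heart disease (for example "Saddle embolus of pulmonary artery with acute cor pulmonale"); I27.24 and I27.82 under chronic lung disease. No I26.9x and no deep vein thrombosis codes. Thrombophilias (D68.5x, D68.6x) are under blood disorders, but they are a risk factor rather than prior thrombosis |
| Peripheral arterial disease | None |
| Dyslipidaemia | None |
| Tobacco use | None |
| Anticoagulants, antiplatelets, statins, antihypertensives | None |

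The codes that are present sit inside single yes/no flags that also cover many other conditions, so neither hypertension nor prior thromboembolism is adjusted for in its own right.

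**Step 2. See what the other provisions recover.**

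- The empiric screen selects on frequency. Hypertension, lipid disorders and common cardiovascular drugs could plausibly rank in the top 25. Stroke/TIA and thromboembolism history are unlikely to. Even a code that ranks is only considered.
- The clean period for MI, PE, both strokes and CVST is days -365 to 0 (Table 2). It removes a prior-year event of the same type. It leaves cross-outcome history, such as a stroke before an MI or a deep vein thrombosis before a PE, and anything older.

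**Step 3. Size.** The protocol gives no event counts, prevalences or effect sizes for these factors, so there is no stated figure to reproduce. What follows is illustration on assumed values. For one omitted binary factor with rate ratio RR for the outcome, and prevalence p1 in recipients and p0 in comparators after matching:

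bias factor = [1 + p1(RR − 1)] / [1 + p0(RR − 1)]

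Less common factor, lower in recipients:

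| p1 / p0 | RR 2 | RR 3 | RR 5 |
|---|---|---|---|
| 5% / 6% | 1.05/1.06 = 0.991 | 1.10/1.12 = 0.982 | 1.20/1.24 = 0.968 |
| 6% / 8% | 1.06/1.08 = 0.981 | 1.12/1.16 = 0.966 | 1.24/1.32 = 0.939 |
| 5% / 8% | 1.05/1.08 = 0.972 | 1.10/1.16 = 0.948 | 1.20/1.32 = 0.909 |

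Common factor, higher in recipients:

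| p1 / p0 | RR 1.5 | RR 3 |
|---|---|---|
| 35% / 30% | 1.175/1.15 = 1.022 | 1.70/1.60 = 1.06 |
| 40% / 30% | 1.20/1.15 = 1.043 | 1.80/1.60 = 1.125 |
| 50% / 30% | 1.25/1.15 = 1.087 | 2.00/1.60 = 1.25 |

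The 50% versus 30% row is a large imbalance to survive matching (standardized difference 0.417) and is shown as an extreme.

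**Step 4. Compare with sampling error.** If each arm had 2,000 events (assumed), the 95% interval half-width on the log scale would be 1.96 × √(2/2000) = 0.062. In the first table only two of the nine cells exceed it: RR 5 at 5%/8% (|ln 0.909| = 0.095) and, barely, RR 5 at 6%/8% (0.0625). The RR 3, 6%/8% cell gives 0.035, well inside.

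**The case against.** The strongest reply is that much vascular risk is already adjusted for. The heart flag covers coronary atherosclerosis, atrial fibrillation and heart failure, and obesity, type 2 diabetes, kidney disorders and chronic lung disease are fixed terms. The printed equation has a place for empiric variables, the clean period removes the most predictive history (a recent event of the same type), and an outcome-specific PS model is allowed for. The SCRI covers the same outcomes and is repeated in the ORD. Section 9.9 discloses residual confounding in general terms. All of this stands as partial mitigation. None of it makes the listed factors fixed terms, and the limitations section does not name vascular risk.

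A second objection is that 6% versus 8% is a standardized difference of 0.02/√[(0.0564 + 0.0736)/2] = 0.078, below the 0.1 tolerance, so it would pass as balanced even if listed. That is correct, and it means the illustration does not measure the gain from the fix. But the tolerance governs what is flagged. A covariate in the PS is adjusted for whether or not it would have been flagged.

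Stronger readings are tempting and should not be made:

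- A reader might infer that no covariate captures hypertension or prior thromboembolism at all. The I11/I13, I26.0x and I27.24/I27.82 codes contradict that.
- A reader might infer that the bias makes the vaccine look protective. The document says nothing on how vascular risk differs between the groups, and the bias could go either way.
- A reader might infer that the vascular outcomes will supply most events, so that the shift would be statistically significant. No event counts are given, and most of the assumed scenarios fall inside the half-width.

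**Conclusion.** The point holds for the Phase 2 cohort in limited form. Seven groups of vascular predictors are left out of the fixed PS terms of a model meant to serve five vascular outcomes, apart from narrow related codes inside broad flags. Their entry depends on a discretionary, frequency-based step, and any imbalance in them would not appear in the balance table.

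The size is not derivable from the document. With one factor and modest assumed imbalance it is a few percent (factors of 0.91 to 1.06); the extreme case shown is 1.25. Several correlated omissions could add to one another, which these one-at-a-time figures do not capture. A shift of this order can move an estimate near 1. A single such factor would not by itself produce the rate ratio above 3.0 in the signal rule. The SCRI is unaffected by time-fixed factors, but only the cohort follows patients for up to a year. This is an inexpensive improvement worth making rather than a flaw that invalidates the study.

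**What to change.** Add to 9.3.3, the PS equation and the balance table, as fixed binary terms: essential hypertension; cerebrovascular disease or TIA, with history codes; deep vein thrombosis and other prior venous thromboembolism, with history codes; peripheral arterial disease; dyslipidaemia; tobacco use; and one-year dispensing of anticoagulants, antiplatelets, statins and antihypertensives.

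If the master cohort cannot be re-matched before the final report planned for 30 April 2026, the minimum is to report the balance of these factors in the matched cohorts and to run a sensitivity analysis adjusting for them in the Poisson models for MI, PE, both strokes and CVST.

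The cost is extra code lists in data already held, a re-fit of the PS and possibly slightly fewer close matches. Capture will be imperfect: tobacco use may be under-recorded in claims, and section 9.9 already notes that medications paid for out of pocket are not observed.
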